### **Statement of Compliance to protocol, GCP and applicable regulatory guidelines:**

This trial will be conducted in compliance with the protocol, ISO 14155, the International Conference on Harmonization Good Clinical Practice E6 (ICH-GCP), the Declaration of Helsinki, and all applicable regulatory requirements.

### CHANGE HISTORY

Version	Originator	Description of Change(s) and Section Number(s) Affected	Date
1.0	[REDACTED]	Original Protocol	04 February 2020
2.0	[REDACTED]	Updated control lens, secondary endpoints/hypothesis, statistical analysis plan, and added Medical Safety Officer to list of approvers	24 April 2020
3.0	[REDACTED]	Added COVID risk mitigation guidelines as Appendix F, Revised eligible age range, updated Section 13.5 regarding pregnancy during the study . Added Step 1.6	28 July 2020

# Clinical Study Protocol

## Johnson & Johnson Vision Care, Inc.

### SYNOPSIS

Protocol Title	Clinical Evaluation of Daily Disposable Etafilcon A Cosmetic Contact Lenses
Sponsor	JJVC, [name]
Clinical Phase	Confirmatory phase, Phase 3
Trial Registration	This study will be registered on ClinicalTrials.gov based on the following: confirmatory study meets the requirements for registration.
Test Article(s)	Investigational Products: etafilcon A with cosmetic pattern
Wear and Replacement Schedules	Wear Schedule: Daily Wear Replacement Schedule: Daily Disposable
Objectives	
The primary objective of this study is to evaluate high luminance/high contrast visual performance (Logarithm of Minimal Angle of Resolution [logMAR]) of two investigational cosmetic lenses at lens fitting.
 
Additional assessments will include:
 
 
• Subjective Vision (CLUE)
 
• Subjective Comfort (CLUE)
 
• Subjective Handling (CLUE)
 
• logMAR objective vision (high luminance/low contrast and low luminance/high contrast)
 
• Mechanical Lens fit
 
• Cosmetic Lens fit/Hula Hoop
 
• Ocular Physiology
 

Study Endpoints	
Primary endpoint: LogMAR visual acuity at fitting using ETDRS charts (CTP-2059).
 
Other observations (descriptively summarized for each lens type) will include: Subjective Vision (CLUE) Subjective Comfort (CLUE) Subjective Handling (CLUE) logMAR objective vision (high luminance/low contrast and low luminance/high contrast) Mechanical Lens fit Cosmetic Lens fit/Hula Hoop Ocular Physiology

# Clinical Study Protocol

## Johnson & Johnson Vision Care, Inc.

Study Design	
This will be a randomized, double-masked, bilateral, cross-over, 2 treatment by 2 period dispensing study. There will be 4 visits. There will be a 2 to 5 day washout period between treatments.
 
Visit 1: Baseline and eligibility, insert treatment #1, logMAR vision, post-fit questionnaire, lens fit assessment. Dispense treatment #1 for 6 (<math>\pm</math>1) days
 
Visit 2: Follow-up on treatment #1: Subjective questionnaire, logMAR vision, lens fit, and physiology assessment. Washout for 2 to 5 days
 
Visit 3: Insert treatment #2, logMAR vision, post-fit questionnaire, lens fit assessment. Dispense treatment #3 for 6 (<math>\pm</math>1) days
 
Visit 4: Follow-up on treatment #2: Subjective questionnaire, logMAR vision, lens fit. Final evaluation.
 
See the flow chart at the end of the synopsis table for the schematic of the study visits and procedures of main observations.

Sample Size	Up to 50 subjects will be enrolled with the aim of approximately 40 subjects completing.
Study Duration	The study is expected to last up to 2 months. The enrollment period will also be up to 3 months.
Anticipated Study Population	
We will aim to recruit up to 50 female subjects, ages 18 to 29 (inclusive). Subject must be habitual contact lens wearers who have purchased and worn cosmetic/circle contact lenses in the last 6 months.
 
We will aim for 60% of the subjects to be self-reported as Asian with Asian eye characteristics

# Clinical Study Protocol

## Johnson & Johnson Vision Care, Inc.

Eligibility Criteria	
Potential subjects must satisfy all of the following criteria to be enrolled in the study:
 

1. The subject must read, understand, and sign the STATEMENT OF INFORMED CONSENT and receive a fully executed copy of the form

2. Females between 18 and 29 (inclusive) years of age at the time of screening

3. Appear able and willing to adhere to the instructions set forth in this clinical protocol (i.e. willing to wear only the study lenses and not use habitual lenses during the dispensing periods)

4. Be a current soft contact lens wearer in both eyes with a minimum of 6 hours/day and 5 days/week over the last month by self-report

5. Be a current wearer of cosmetic/circle lenses in the last 6 months, by self-report.

6. The subject must be willing to be photographed and/or video-taped

 
Inclusion Criteria After Baseline
 

7. The subject's vertex corrected spherical equivalent distance refraction must be in the range of -1.00 D to -6.00 D (inclusive) in each eye

8. The subject's refractive cylinder must be less than or equal to 0.75 D (inclusive) in each eye

9. Have spherical best corrected visual acuity of 20/25 or better in each eye

----------------------	---

# Clinical Study Protocol

## Johnson & Johnson Vision Care, Inc.

	
Potential subjects who meet any of the following criteria will be excluded from participating in the study:
 
 
1. Currently pregnant or lactating
 
2. Any systemic disease (eg, Sjögren’s Syndrome), allergies, infectious disease (eg, hepatitis, tuberculosis), contagious immunosuppressive diseases (eg, HIV), autoimmune disease (eg rheumatoid arthritis), or other diseases, by self-report, which are known to interfere with contact lens wear and/or participation in the study (at the investigators discretion)
 
3. Use of systemic medications (eg, chronic steroid use) that are known to interfere with contact lens wear (at the investigators discretion)
 
4. Any previous, or planned (during the study) ocular surgery (eg, radial keratotomy, PRK, LASIK, etc.)
 
5. Any previous history or signs of a contact lens-related corneal inflammatory event (eg, past peripheral ulcer or round peripheral scar), or any other ocular abnormality that would contraindicate contact lens wear (at the investigators discretion)
 
6. Participation in any contact lens or lens care product clinical trial within seven (7) days prior to study enrollment.
 
7. Employee or family members of clinical site (eg, Investigator, Coordinator, Technician) Exclusion Criteria after Baseline
 
 
Eligibility after Baseline:
 
 
8. Any ocular allergies, infections or other ocular abnormalities that are known to interfere with contact lens wear and/or participation in the study. This may include, but not be limited to entropion, ectropion, extrusions, chalazia, recurrent styes, glaucoma, history of recurrent corneal erosions, aphakia, or corneal distortion (at the investigators discretion)
 
9. Clinically significant (Grade 3 or 4 on FDA scale) tarsal abnormalities, bulbar injection, corneal edema, corneal vascularization, corneal staining, or any other abnormalities of the cornea which would contraindicate contact lens wear.
 

Disallowed Medications/Interventions
	
See section 9.1

# Clinical Study Protocol

[figure not shown]
## Johnson & Johnson Vision Care, Inc.

Measurements and Procedures	logMAR visual acuity, PRO questionnaires (comfort, vision, and handling), lens fit assessment, cosmetic lens fit assessment/hula hoop assessment, and safety parameters (slit lamp findings, entrance/exit visual acuity).
Microbiology or Other Laboratory Testing	None
Study Termination	The occurrence of one or more Unanticipated Adverse Device Effect (UADE), or any SAE where relationship to study agent cannot be ruled out, will result in stopping further dispensing investigational product. In the event of a UADE or SAE, the Sponsor Medical Monitor may unmask the treatment regimen of subject(s) and may discuss this with the Principal Investigator before any further subjects are enrolled.
Ancillary Supplies/ Study-Specific Materials	Tears Naturale re-wetting drops, FluStrips fluorescein strips, Bausch & Lomb Sensitive Eyes plus Saline, or alternative products approved by the Sponsor.
Principal Investigator(s) and Study Institution(s)/Site(s)	A full list of Principal Investigators, clinical sites, and institutions is kept separately from the Study Protocol and is included in the study Trial Master File.

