# Clinical Study Protocol

## Johnson & Johnson Vision Care, Inc.

PIG	Patient Instruction Guide
PQC	Product Quality Complaint
PRO	Patient Reported Outcome
PVP	Polyvinylpyrrolidone
QA	Quality Assurance
QC	Quality Control
SAE	Serious Adverse Event/Serious Adverse Experience
SAP	Statistical Analysis Plan
SAS	Statistical Analysis System
SD	Standard Deviation
SOP	Standard Operating Procedure
UADE	Unanticipated Adverse Device Effect
USADE	Unanticipated Serious Adverse Device Effect
VA	Visual Acuity

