### **11. STUDY TERMINATION**

The occurrence of one or more Unanticipated Serious Adverse Device Effect (USADE), or any SAE where the relationship to study agent cannot be ruled out, may result in stopping further dispensing of test article. In the event of a USADE or SAE, the Sponsor may unmask the treatment regimen for the subject(s) and will discuss this with the Investigator before any further subjects are enrolled.

The Sponsor will determine when a study will be stopped. The Principal Investigator always has the discretion to initiate stopping the study based on patient safety or if information indicates the study's results are compromised.

JJVC reserves the right to terminate the study at any time for any reason. Additionally, the IEC/IRB reserves the right to terminate the study if an unreasonable risk is determined. The study can be terminated by the Principal Investigator at the individual clinical site due to specific clinical observations, if in their opinion, after a discussion with JJVC, it is determined that it would be unwise to continue at the clinical site.

JJVC (and the IEC/IRB and DMC, if applicable) will evaluate all adverse events. If it is determined that an adverse event presents an unreasonable risk, the investigation, or that part of the investigation presenting the risk, will be terminated as soon as possible.

Should the study be terminated (either prematurely or as scheduled), the Investigator will notify the IEC/IRB and Regulatory Authority as required by local regulatory requirements.

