# Clinical Study Protocol

## Johnson & Johnson Vision Care, Inc.

- Limbal cell Damage leading to Conjunctivalization

**Significant Adverse Events** – are defined as events that are symptomatic and warrant discontinuation (temporary or permanent) of the contact lens wear

Diagnoses and conditions that are considered Ocular Significant Adverse Events include, but not limited to the following:

- Contact Lens Induced Peripheral Ulcer (CLPU)
- Significant Infiltrative Events (SIE)
- Superior Epithelial Arcuate Lesions (SEALs)
- Any Temporary Loss of > 2 Lines of BSCVA
- Other grade 3 or higher corneal findings, such as abrasions or edema
- Non-contact lens related corneal events - e.g. Epidemic Keratoconjunctivitis (EKC)
- Asymptomatic Corneal Scar
- Any corneal event which necessitates temporary lens discontinuation > 2 weeks

**Non-Significant Adverse Events** – are defined as those events that are usually asymptomatic and usually do not warrant discontinuation of contact lens wear but may cause a reduction in wear time. However, the Investigator may choose to prescribe treatment as a precautionary measure.

Diagnoses and conditions that are considered Ocular Non-Significant Adverse Events include, but not limited to the following:

- Non-significant Infiltrative Event (NSIE)
- Contact Lens Papillary Conjunctivitis (CLPC)
- Superficial Punctate Keratitis (SPK)
- Conjunctivitis: Bacterial, Viral, Allergic
- Blepharitis
- Meibomianitis
- Contact Dermatitis
- Localized Allergic Reactions
- Any corneal event not explicitly defined as serious or significant adverse event, which necessitates temporary lens discontinuation < 2 weeks

**Adverse Device Effect (ADE)** – An ADE is an “adverse event related to the use of an investigational medical device.

**NOTE 1: to entry: This definition includes adverse events resulting from insufficient or inadequate instructions for use, deployment, implantation, installation, or operation, or any malfunction of the investigational medical device.**

**NOTE 2 to entry: This definition includes any event resulting from use error or from intentional misuse of the investigational medical device.”**

**Unanticipated Adverse Device Effect (UADE)** – Any serious adverse effect on health or safety or any life-threatening problem or death caused by, or associated with, the test article,

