### **Unanticipated (Serious) Adverse Device Effect (UADE)**

In the event of an Unanticipated (Serious) Adverse Device Effect (UADE), the Investigator will submit a report of the UADE to the Sponsor and IEC/IRB as soon as possible, but no later than 24 hours after the Investigator first learns of the effect. This report is in addition to the immediate notification mentioned above.

The Sponsor must conduct an evaluation of the UADE and must report the results of the evaluation to FDA, the IEC/IRB and participating Investigators within 10 working days after the Sponsor first receives notification of the effect.

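### After an SAE whose link to the study lenses cannot be ruled out, the synopsis requires dispensing to stop and Section 11 only permits it; no clause says which governs

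*Combined protocol and SAP*

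**What the plan says.** The Study Termination row of the synopsis has two triggers: one or more UADE, or any SAE for which a relationship to the study agent cannot be ruled out. Either one "will result in stopping further dispensing investigational product". The Sponsor Medical Monitor may then unmask and "may discuss this with the Principal Investigator before any further subjects are enrolled".

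Section 11 (Study Termination) gives the same SAE trigger and puts USADE in place of UADE. Here the event "may result in stopping further dispensing of test article". The Sponsor may unmask and "will discuss this with the Investigator before any further subjects are enrolled".

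Section 11 adds that "The Sponsor will determine when a study will be stopped". It also provides that if an adverse event is judged to present an unreasonable risk, the investigation, or the part of it that carries the risk, must be terminated promptly.

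On terms, the abbreviation list expands USADE as "Unanticipated Serious Adverse Device Effect" and lists it separately from UADE. Section 13.1 defines only UADE, which begins: "Any serious adverse effect on health or safety or any life-threatening problem or death caused by, or associated with, the test article".

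**The concern.** A rule that stops dispensing for safety should give one answer when its trigger is met. Here the synopsis makes the stop automatic and Section 11 makes it a matter of judgement, on identical SAE wording.

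IEC/IRB approval does not settle the point. Under Section 18.3 the committee approves the final protocol, and that contains both sentences.

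The gap also affects compliance. Section 10 prohibits waivers and treats a deviation that could affect patient safety as major and reportable to the IEC/IRB. A site that keeps dispensing after a qualifying SAE departs from the synopsis but complies with Section 11. The investigator, the monitor and the committee could not tell from the document whether a reportable deviation had occurred.

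**Working it through.** No figure is involved, so the check is a comparison of the two texts.

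| Element | Synopsis | Section 11 | Agree? |
|---|---|---|---|
| SAE trigger | relationship cannot be ruled out | the same | yes |
| Device-effect trigger | UADE | USADE | probably |
| Stop dispensing | *will* | *may* | no |
| Unmask | *may* | *may* | yes |
| Discuss before further enrolment | *may* | *will* | no |
| Who acts | Sponsor Medical Monitor | Sponsor | compatible |

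**Status of the texts.** Both are current protocol text. Neither belongs to the change history, and neither is redacted at this point.

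**Object of the stop.** The synopsis refers to investigational product and Section 11 to test article. Section 1.1 calls both lenses investigational, and Table 1 lists both as test articles, so this is not a difference in scope.

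**Device-effect trigger.** USADE has no definition of its own in Section 13. UADE is already defined as a serious effect, and the relevant heading in Section 13.4.1 puts the word serious in brackets before the UADE abbreviation. The two terms are very likely the same thing, though the protocol does not say so.

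**Search for a reconciling clause.** The sentence "The Sponsor will determine when a study will be stopped" concerns stopping the study, not whether dispensing must cease after a qualifying event. The unreasonable-risk clause is mandatory, but it starts from a judgement about risk, not from the occurrence of an SAE. No clause ranks the synopsis against the body.

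**Worked case.** Section 13.1 lists iritis as an ocular SAE. Section 1.4 lists it among the known risks of soft lenses, so it would normally enter through the SAE trigger and not as an unanticipated effect. Suppose the investigator grades it possibly related. Section 13.2.1 says that in this category a causal link cannot be excluded, so the trigger is met. Under the synopsis dispensing stops; under Section 11 it need not.

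**The case against.** The strongest reply is that the two texts are compatible in practice. Section 11 permits a stop and does not forbid one. Stopping and then holding the discussion satisfies both, so nobody is forced to breach either. This stands. A reader might infer that the protocol imposes contradictory duties, and it does not. What remains is the risk that someone follows the permissive sentence and overlooks the mandatory one.

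Second, the reversal about the discussion may be smaller than it looks. In both places the discussion follows directly on the optional unmasking and refers back with the word *this*, which may mean only the unmasking. A reader might infer a dropped duty to discuss the event itself; the wording does not establish that. The verbs still differ.

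Third, a reader might infer that under Section 11 other subjects are left unprotected. They are not:
- Serious events reach the Sponsor within 24 hours (Section 13.4).
- The medical monitor joins the investigator in categorising them (Section 13.2).
- A subject whose serious event ends lens wear is withdrawn (Section 8.2).
- The Sponsor and the Principal Investigator can act to stop the study (Section 11).
- Any part presenting an unreasonable risk must be terminated (Section 11).

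These make it unlikely that a site would choose between the sentences alone. None of them says whether one qualifying SAE obliges a stop for others.

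Fourth, one might go on to ask for a study-wide hold, a bar on replacement lenses or a formal restart step. Neither text contains these. They would be design preferences and do not follow from the inconsistency.

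**Conclusion.** The inconsistency is real and should be corrected. The protocol gives a mandatory and a discretionary form of the same stopping rule, reverses the verb on the discussion as well, and does not say which form governs.

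Its size is modest. One qualifying SAE is enough to expose it, but Section 1.5 reports no serious or unanticipated adverse events in earlier studies of etafilcon A with PVP cosmetic lenses, so the trigger should be rare. The effect is on safety conduct only. The number of dispensings scheduled does not measure the defect, because it says nothing about how many would be affected.

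The conclusion rests on reading both passages as operative and on the absence of any precedence clause in the documents available. It does not depend on UADE and USADE being different, since the SAE trigger alone produces the conflict.

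**What to change.** Put one identical pair of sentences in the synopsis and Section 11, and use UADE as defined in Section 13.1 in both.

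- First sentence: one or more UADE, or any SAE whose relationship to the study agent cannot be ruled out, leads to a mandatory stop in further dispensing of test article. This keeps the synopsis verb.
- Second sentence: the Sponsor may unmask the affected subject or subjects, and must hold the discussion with the Investigator before further enrolment. This keeps the Section 11 verb.

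This version meets both current texts, because a required action is always allowed where the text says *may*. If the sponsor intends a discretionary stop, *may* in both places would also be consistent. That would relax what the synopsis now requires, and the IEC/IRB should see it as such.

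The drafting cost is a wording change in two places, submitted as a protocol revision under Section 18.3.

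The operational cost is that dispensing stops after a single qualifying event, as the synopsis already demands. A subject on washout day *d* when a stop of *H* days begins reaches Visit 3 no earlier than day *d* + *H*, and leaves the 2 to 5 day window of Table 3 once that exceeds 5. For example, day 3 plus a 3-day stop gives day 6. The documents set no length for a stop. Section 13.4.1 says the Sponsor "must report the results of the evaluation to FDA, the IEC/IRB and participating Investigators within 10 working days", but that is a reporting deadline for UADEs and should not be read as the length of a hold.

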# Clinical Study Protocol

## Johnson & Johnson Vision Care, Inc.

[figure not shown]
[figure not shown]
Figure 1: Study Flowchart

# Clinical Study Protocol

## Johnson & Johnson Vision Care, Inc.

### COMMONLY USED ABBREVIATIONS AND DEFINITIONS OF TERMS

ADD	Plus Power Required For Near Use
ADE	Adverse Device Effect
AE	Adverse Event/Adverse Experience
BCVA	Best Corrected Visual Acuity
BSCVA	Best Spectacle Corrected Visual Acuity
CFR	Code of Federal Regulations
CLUE	Contact Lens User Experience
COAS	Complete Ophthalmic Analysis System
COM	Clinical Operations Manager
CRA	Clinical Research Associate
CRF	Case Report Form
CRO	Contract Research Organization
CT	Center Thickness
	
D	Diopter
DMC	Data Monitoring Committee
eCRF	Electronic Case Report Form
EDC	Electronic Data Capture
ETDRS	Early Treatment Diabetic Retinopathy Study
FDA	Food and Drug Administration
GCP	Good Clinical Practice
HIPAA	Health Insurance Portability and Accountability Act
IB	Investigator's Brochure
ICF	Informed Consent Form
ICH	International Conference on Harmonization
IDE	Investigational Device Exemption
IEC	Independent Ethics Committee
IRB	Institutional Review Board
ISO	International Organization for Standardization
ITT	Intent-to-Treat
JJVC	Johnson & Johnson Vision Care, Inc.
LC	Limbus Center
LogMAR	Logarithm of Minimal Angle of Resolution
MedDRA ®	Medical Dictionary for Regulatory Activities
MOP	Manual of Procedures
NIH	National Institutes of Health
OD	Right Eye
OHRP	Office for Human Research Protections
OHSR	Office for Human Subjects Research
OS	Left Eye
OU	Both Eyes
PD	Protocol Deviation
PHI	Protected Health Information
PI	Principal Investigator

# Clinical Study Protocol

## Johnson & Johnson Vision Care, Inc.

PIG	Patient Instruction Guide
PQC	Product Quality Complaint
PRO	Patient Reported Outcome
PVP	Polyvinylpyrrolidone
QA	Quality Assurance
QC	Quality Control
SAE	Serious Adverse Event/Serious Adverse Experience
SAP	Statistical Analysis Plan
SAS	Statistical Analysis System
SD	Standard Deviation
SOP	Standard Operating Procedure
UADE	Unanticipated Adverse Device Effect
USADE	Unanticipated Serious Adverse Device Effect
VA	Visual Acuity

